9.11 SUBJECTS

Please refer to [Section 9.2.1](#) (Selection of study population).

9.11.1 Cases

n.a

9.11.2 Controls

n.a

9.12 BIAS

Methodological efforts have been taken to minimize selection bias: these efforts include the recommendation to include consecutive patients meeting each of the inclusion criteria and none of the exclusion criteria. In addition, this possible selection bias may be limited by the retrospective aspect of the data collection, data that have been already collected at the time of the study.

10. PROTECTION OF HUMAN SUBJECTS

10.1 INFORMED CONSENT, DATA PROTECTION, STUDY RECORDS

The study will be carried out in compliance with the protocol, the principles laid down in the Declaration of Helsinki, in accordance with the International Conference on Harmonisation (ICH) Harmonized Tripartite Guideline for GCP (to the extent applicable to the NIS setting and required by local regulations), Good Epidemiological Practice (GEP), Guidelines for Good Pharmacoepidemiology Practice (GPP), and relevant BI SOPs. Standard medical care (prophylactic, diagnostic and therapeutic procedures) remains in the responsibility of the treating investigator of the patient.

The investigator should inform the sponsor immediately of any urgent safety measures taken to protect the study subjects against any immediate hazard, and also of any serious breaches of the protocol, ICH GCP and Japanese GCP regulations (Ministry of Health and Welfare Ordinance No. 28, March 27, 1997).

The rights of the investigator and of the sponsor with regard to publication of the results of this trial are described in the investigator contract. As a general rule, no trial results should be published prior to finalisation of the Study Report.

10.1.1 Study approval, patient information, and informed consent

This study will be initiated only after all required legal documentation has been reviewed and approved by the respective IRB / IEC and competent authority (CA) according to national and international regulations. The same applies for the implementation of changes introduced by amendments.

In some countries, retrospective observational studies can be exempt from a written informed consent per local regulations and legal requirements, IRB / IEC often grants a waiver of consent for retrospective chart review studies. In order to avoid bias by exclusion of subjects that cannot be given informed consent for any reason like death, missing contact information etc., exempt from a written informed consent should be asked for such situations.

In case such a waiver is not given, prior to patient participation in the study, written informed consent must be obtained from each patient (or the patient's legally accepted representative) according to ICH GCP and to the regulatory and legal requirements of the participating country.

Each signature must be personally dated by each signatory and the informed consent and any additional patient-information form retained by the investigator as part of the trial records. A signed copy of the informed consent and any additional patient information must be given to each patient or the patient's legally accepted representative.

The patient must be informed that his / her medical records may be examined by authorised monitors (CML / CRA) or Clinical Quality Assurance auditors appointed by Boehringer Ingelheim, by appropriate IRB / IEC members, and by inspectors from regulatory authorities.

11. MANAGEMENT AND REPORTING OF ADVERSE EVENTS/ADVERSE DRUG REACTIONS

11.1 DEFINITIONS OF ADVERSE EVENTS

Adverse event

An adverse event (AE) is defined as any untoward medical occurrence in a patient or clinical investigation subject administered a medicinal product and which does not necessarily have a causal relationship with this treatment. An AE can therefore be any unfavourable and unintended sign (e.g. an abnormal laboratory finding), symptom, or disease temporally associated with the use of a medicinal product, whether or not considered related to the medicinal product.

Adverse reaction

An adverse reaction is defined as a response to a medicinal product which is noxious and unintended. Response in this context means that a causal relationship between a medicinal product and an adverse event is at least a reasonable possibility. Adverse reactions may arise from use of the product within or outside the terms of the marketing authorisation or from occupational exposure. Conditions of use outside the marketing authorization include off-label use, overdose, misuse, abuse and medication errors.

Serious adverse event

A serious adverse event (SAE) is defined as any AE which

- results in death,
- is life-threatening,
- requires in-patient hospitalization, or
- prolongation of existing hospitalisation,
- results in persistent or significant disability or incapacity, or
- is a congenital anomaly/birth defect

Life-threatening in this context refers to a reaction in which the patient was at risk of death at the time of the reaction; it does not refer to a reaction that hypothetically might have caused death if more severe.

Medical and scientific judgment should be exercised in deciding whether other situations should be considered serious reactions, such as important medical events that might not be immediately life threatening or result in death or hospitalization but might jeopardize the patient or might require intervention to prevent one of the other outcomes listed above. Examples of such events are intensive treatment in an emergency room or at home for allergic bronchospasm, blood dyscrasias or convulsions that do not result in hospitalization or development of dependency or abuse. Any suspected transmission via a medicinal product of an infectious agent is also considered a serious adverse reaction.

For Japan, an AE which possibly leads to disability will be reported as an SAE.

Adverse Event of Special Interest (AESI)

Protocol for non-interventional studies based on existing data

BI Study Number 1200.270

c09038525-01

Proprietary confidential information © 2016 Boehringer Ingelheim International GmbH or one or more of its affiliated companies

The term AESI relates to any specific AE that has been identified at the project level as being of particular concern for prospective safety monitoring and safety assessment within this study, e.g. the potential for AEs based on knowledge from other compounds in the same class.

No AESIs have been defined for this study.

11.2 ADVERSE EVENT AND SERIOUS ADVERSE EVENT COLLECTION AND REPORTING

The investigator shall maintain and keep detailed records of all AEs in their patient files.

Collection of AEs

The study design is of non-interventional nature and the study is conducted within the conditions of the approved marketing authorization. Sufficient data from controlled interventional trials are available to support the evidence on the safety and efficacy of the studied BI drug. For this reason the following AE collection and reporting requirements have been defined.

The following must be collected by the investigator in the eCRF from signing the informed consent onwards until the end of the study:

- all ADRs (serious and non-serious)
- all AEs with fatal outcome
- for Japan: an AE which possibly leads to disability will be reported as an SAE

All ADRs, including those persisting after study completion must be followed up until they are resolved, have been sufficiently characterized, or no further information can be obtained.

The investigator carefully assesses whether an AE constitutes an ADR using the information below.

Causal relationship of AEs

The definition of an adverse reaction implies at least a reasonable possibility of a causal relationship between a suspected medicinal product and an adverse event (AE). An adverse reaction, in contrast to an AE, is characterized by the fact that a causal relationship between a medicinal product and an occurrence is suspected.

Medical judgment should be used to determine the relationship, considering all relevant factors, including pattern of reaction, temporal relationship, de-challenge or re-challenge, confounding factors such as concomitant medication, concomitant diseases and relevant history.

Arguments that may suggest a **reasonable causal relationship** could be:

- The event is **consistent with the known pharmacology** of the drug
- The event is known to be caused by or **attributed to the drug class**.
- **A plausible time to onset of the event** relative to the time of drug exposure.
- Evidence that the **event is reproducible** when the drug is re-introduced

Protocol for non-interventional studies based on existing data

BI Study Number 1200.270

c09038525-01

Proprietary confidential information © 2016 Boehringer Ingelheim International GmbH or one or more of its affiliated companies

- **No medically sound alternative etiologies** that could explain the event (e.g. preexisting or concomitant diseases, or co-medications).
- The event is typically **drug-related and infrequent in the general population** not exposed to drugs (e.g. Stevens-Johnson syndrome).
- An indication of dose-response (i.e. greater effect size if the dose is increased, smaller effect size if dose is diminished).

Arguments that may suggest that there is **no reasonable possibility of a causal relationship** could be:

- No plausible time to onset of the event relative to the time of drug exposure is evident (e.g. pre-treatment cases, diagnosis of cancer or chronic disease within days/weeks of drug administration; an allergic reaction weeks after discontinuation of the drug concerned)
- Continuation of the event despite the withdrawal of the medication, taking into account the pharmacological properties of the compound (e.g. after 5 half-lives). Of note, this criterion may not be applicable to events whose time course is prolonged despite removing the original trigger.
- Additional arguments amongst those stated before, like alternative explanation (e.g. situations where other drugs or underlying diseases appear to provide a more likely explanation for the observed event than the drug concerned).
- Disappearance of the event even though the study drug treatment continues or remains unchanged.

Intensity of AEs

The intensity of adverse events should be classified and recorded according to the CTCAE criteria (version 4.0) ([R15-5988](#)) in the eCRF.

Pregnancy

In rare cases, pregnancy might occur in a study. Once a subject has been enrolled into the study, after having taken Gi(l)otrif[®] the investigator must report any drug exposure during pregnancy, which occurred in a female subject or in a partner to a male subject to the Sponsor by means of Part A of the Pregnancy Monitoring Form. The outcome of the pregnancy associated with the drug exposure during pregnancy must be followed up and reported by means of Part B of the Pregnancy Monitoring Form.

The ISF will contain the Pregnancy Monitoring Form for Clinical Trials (Part A and Part B).

In the absence of a reportable AE, only the Pregnancy Monitoring Form must be completed, otherwise the NIS AE form is to be completed and forwarded as well within the respective timelines.

Expedited Reporting of AEs and Drug Exposure During Pregnancy

The following must be reported by the investigator on the NIS AE form from signing the informed consent onwards until the end of the study:

Type of Report	Timeline
----------------	----------

Protocol for non-interventional studies based on existing data

BI Study Number 1200.270**c09038525-01**

Proprietary confidential information © 2016 Boehringer Ingelheim International GmbH or one or more of its affiliated companies

All Serious Adverse Drug Reactions (SADRs) associated with Gi(l)otrif [®]	immediately within 24 hours
All AEs with fatal outcome in patients exposed to Gi(l)otrif [®]	immediately within 24 hours
For Japan: AE which possibly leads to disability in patients exposed to Gi(l)otrif [®]	immediately within 24 hours
All non-serious ADRs associated with Gi(l)otrif [®]	7 calendar days
All pregnancy monitoring forms	7 calendar days

The same timelines apply if follow-up information becomes available for the respective events. In specific occasions the physician could inform the sponsor upfront via telephone. This does not replace the requirement to complete and fax the NIS AE form.

Information required

For each reportable AE, the investigator should provide the information requested on the appropriate eCRF pages and the NIS AE form.

Reporting of related AEs associated with any other BI drug

The investigator is encouraged to report all AEs related to any BI drug other than Gi(l)otrif[®] according to the local regulatory requirements for spontaneous AE reporting at the investigator's discretion by using the locally established routes and AE report forms. The term AE includes drug exposure during pregnancy, and, regardless of whether an AE occurred or not, any abuse, off-label use, misuse, medication error, occupational exposure, lack of effect, and unexpected benefit.

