9. RESEARCH METHODS

9.1 STUDY DESIGN

This is a non-interventional, multi-country, multi-site study based on existing data from medical records of patients treated with Gi(l)otrif[®] as part of the routine treatment according to the approved label.

Key study outcomes are:

- Effects of Gi(l)otrif[®] dose reduction on frequency of ADRs, and time on treatment, time to progression
- Proportion of patients starting with modified Gi(l)otrif[®] dose and the underlying reason(s)

Data on diagnosis, gender, date of birth, ethnicity, body weight and height, Eastern Cooperative Oncology Group performance score (ECOG) ([R14-0080](#)), EGFR mutational subgroup (Del19/L858R), starting dose of Gi(l)otrif[®], start date of Gi(l)otrif[®] treatment, dose modifications with date, ADRs, concomitant medications (limited to medication for management of diarrhea, skin effects, mucositis/stomatitis as dichotomous variables (e.g. received anti-diarrhea medication yes/no), reason for dose modification of Gi(l)otrif[®], treatment duration of Gi(l)otrif[®], time to progression and type of progression (clinical, radiographic or both clinical/radiographic progression) will be collected from patients medical records by investigators.

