9.2.1 Selection of study population

Site selection:

Sites in countries with launch dates prior to 1st Jan 2015 and known to prescribe Gi(l)otrif[®] on a regular basis will be chosen. Asian and Non-Asian countries will be included.

Inclusion criteria:

All consecutive patients will be included if all the following criteria are present:

- Age \geq 18 years

Protocol for non-interventional studies based on existing data

BI Study Number 1200.270

c09038525-01

Proprietary confidential information © 2016 Boehringer Ingelheim International GmbH or one or more of its affiliated companies

- Patients with EGFR mutation (common mutations), TKI-naïve advanced NSCLC, treated with Gi(l)otrif[®] as the first-line treatment for NSCLC within the approved label
- Signed and dated written informed consent per regulations. (Exemption of a written informed consent for retrospective observational studies in some countries per local regulations and legal requirements.)

Exclusion criteria:

Patient won't be included if any of the following criteria is present:

- Any contraindication to Gi(l)otrif[®] as specified in label.
- Patients with uncommon mutations are excluded as uncommon mutations are not within label in all participating countries (e.g. USA).
- Patients still on treatment with Gi(l)otrif[®] will be excluded unless treatment period is ≥ 6 months.
- Patients treated with Gi(l)otrif[®] within an interventional trial.

A log of all patients included into the study will be maintained in the ISF at the investigational site.

Patients treated with Gi(l)otrif[®] in interventional trials are excluded to ensure the non-interventional setting of this study. The threshold of ≥ 6 months treatment with Gi(l)otrif[®] for patients being still on treatment was chosen to avoid early censoring and enable collection of mature data on ADRs and treatment duration. However, patients who stopped Gi(l)otrif[®] < 6 months will be included to avoid bias. All patients fulfilling inclusion and exclusion criteria from a site will be entered to avoid bias. The maximum of 15 patients per site was chosen to avoid bias by high proportion of patients coming from one site.

BI reserves the right to discontinue the study overall or at a particular study site at any time for the following reasons:

1. Failure to meet expected enrolment goals overall or at a particular study site.

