9.3 VARIABLES

Data will be documented from the date of first dose of Gi(l)otrif[®] treatment until the date of last dose of Gi(l)otrif[®] treatment or end of data collection whichever occurs first.

During the data collection period, the following data will be collected from medical records in an eCRF by investigators during the study:

- Informed consent
- Diagnosis
- Demographics (gender, date of birth, ethnicity)
- Body weight and height at start of Gi(l)otrif[®] treatment
- ECOG performance score at start of Gi(l)otrif[®] treatment
- EGFR mutational subgroup (Del19/L858R)
- Starting dose of Gi(l)otrif[®]
- Start date of Gi(l)otrif[®] treatment
- End date of Gi(l)otrif[®] treatment
- Gi(l)otrif[®] dose modification(s) and date(s)
- ADRs
- Concomitant medications (limited to medication for management of diarrhea, skin effects, mucositis/stomatitis as dichotomous variables (e.g. received anti-diarrhea medication yes/no))
- Reason for dose modification(s)
- Date of progression
- Type of progression:
 - a. clinical
 - b. radiographic
 - c. both clinical/radiographic progression

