9.3.2 Outcomes

9.3.2.1 Primary outcomes

Safety outcomes:

- Percentage of subjects with adverse drug reactions (ADRs) by severity class

Effectiveness outcomes:

- Time on treatment with Gi(1)otrif[®]
- Time to progression with Gi(1)otrif[®]

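### Protocol Sections 11.2 and 9.3 set different eCRF windows for adverse drug reactions, a primary outcome, and nothing says which one governs

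*Protocol*

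**What the plan says.** Two sections of the protocol tell investigators what to enter in the eCRF.

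- **Section 11.2**, which covers all ADRs and all fatal adverse events: "The following must be collected by the investigator in the eCRF from signing the informed consent onwards until the end of the study". A separate sentence sets the same start for expedited reporting: "The following must be reported by the investigator on the NIS AE form from signing the informed consent onwards until the end of the study".
- **Section 9.3**, whose list of eCRF items includes ADRs: "Data will be documented from the date of first dose of Gi(l)otrif[®] treatment until the date of last dose of Gi(l)otrif[®] treatment", or until end of data collection if that is earlier.

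Four other places bear on the conflict.

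- Section 9.1 describes a "study based on existing data from medical records of patients treated with" the drug.
- Section 9.2.1 says that patients still on treatment "will be excluded unless treatment period is ≥ 6 months". Patients who have already stopped may enter whatever their duration.
- Section 10.1.1 expects that some patients will have no consent date: "IRB / IEC often grants a waiver of consent for retrospective chart review studies".
- The first primary outcome in Section 9.3.2.1 is "Percentage of subjects with adverse drug reactions (ADRs) by severity class". Section 9.7.1 adds a comparison of ADRs before and after dose modification, for modifications in the first 6 months of treatment.

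The SAP uses the consent date as well. For a completely missing AE onset date, its imputation interval starts at the earlier of the AE end date and the consent date.

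**The concern.** Section 11.2 is worded for a prospective study, where consent precedes exposure. Here the order is reversed, and the two sections define different sets of ADRs for the same database. If some sites follow one and some the other, ascertainment varies by site, and the ADR percentages set beside LUX-Lung 3 would be too low by an unknown amount. The pre/post-modification comparison is the most exposed, because its pre-modification ADRs arise early in treatment.

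Fatal adverse events are also affected. They are not on the Section 9.3 list, so Section 11.2 is the only stated rule for collecting them. Section 9.7.1 counts death in time to progression.

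**Working it through.** **No planned figure to reproduce.** The documents give no number for the share of ADRs that falls before or after consent. The conflict is established from the text, and the size is then explored on stated assumptions.

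**Step 1: the windows side by side.**

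| | Section 9.3 | Section 11.2, read literally |
|---|---|---|
| Start | first dose | consent signature |
| End | last dose or end of data collection | end of study |
| Patient who stopped before consent | all on-treatment ADRs | no on-treatment ADR onsets |
| Patient still on treatment | all ADRs so far | none from at least the first 6 months |
| Patient under a waiver | all on-treatment ADRs | start not defined |

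The last two columns differ on every ADR that starts in the first 6 months. This assumes that eligibility is already met when consent is signed. Section 9.7.1 restricts the pre/post comparison to modifications in those same 6 months, so the literal Section 11.2 window leaves it no pre-modification ADR onsets. Section 7 reports that 86% of LUX-Lung 3 dose reductions fell in that period.

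**Step 2: how much person-time follows consent.** Inputs:

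- Median time on treatment m: 11.1 or 13.6 months. These are the LUX-Lung 3 median PFS values in Section 7 (all patients; common mutations), used as a proxy.
- Time C from first dose to consent: uniform on 6 to 33 months (assumed). First approval was 12 July 2013 and data collection starts 31 May 2016, which is 34.6 months.
- Time W from consent to end of study: 3.5 or 7 months. 31 May to 31 December 2016 (Section 6) is 7.0 months at most.
- Exponential treatment duration (assumed), with rate λ = ln 2 / m.

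Share still on treatment at consent: S = (e^(−6λ) − e^(−33λ)) / (27λ).

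- m = 11.1: λ = 0.0624, S = (0.6875 − 0.1274) / 1.686 = 0.332, so 67% have stopped.
- m = 13.6: λ = 0.0510, S = (0.7365 − 0.1860) / 1.376 = 0.400, so 60% have stopped.

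Share of on-treatment person-time after consent: S(1 − q) / (1 − Sq), with q = e^(−λW).

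| m | W | q | Calculation | After consent | Outside window |
|---|---|---|---|---|---|
| 11.1 | 3.5 | 0.804 | 0.0652 / 0.7330 | 8.9% | 91.1% |
| 11.1 | 7 | 0.646 | 0.1176 / 0.7854 | 15.0% | 85.0% |
| 13.6 | 3.5 | 0.837 | 0.0654 / 0.6653 | 9.8% | 90.2% |
| 13.6 | 7 | 0.700 | 0.1200 / 0.7200 | 16.7% | 83.3% |

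**Step 3: sensitivity.** A simulation varied the inputs more widely: treatment starts from 12 July 2013 or from 31 December 2014, medians of 8 to 18 months, and consent on 31 May 2016 or spread evenly to 31 December 2016. Between 5.8% and 30.0% of person-time fell after consent, so 70% to 94% fell outside. With front-loaded ADR onset (86% by month 6, borrowing the timing of dose reductions), 0.4% to 2.5% of onsets fell after consent, so 97.5% to 99.6% fell outside.

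**Step 4: the SAP rule.** Take an ADR with no onset date and first dose before both the AE end date and consent. The interval then starts after first dose, and the SAP imputes onset at the interval start. If the end date is missing or later than consent, onset becomes the consent date, possibly after the dose modification or after treatment ended. If the ADR ended before consent, onset becomes its own end date. For a waiver patient the consent term is missing.

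**The case against.** The best defence is that the plan as a whole clearly intends ADRs from first dose. Section 9.1 has ADRs abstracted from medical records. Section 9.2.1 justifies the 6-month rule by the wish for mature ADR data. The Section 9.7.1 pre/post analysis would be unworkable otherwise. Section 10.1.1 seeks waivers so that patients who have died are not excluded, and they could have no ADRs after consent. The SAP's minimum of end date and consent date allows for AEs that ended before consent. Section 11.2 could also be read as saying when the investigator's duty to enter data begins. Training, the site initiation visit and source verification in about 30% of patients might catch misreadings.

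Most of this stands as evidence of intent. A reader might infer that Section 11.2 forbids entering earlier ADRs. The text does not support that: it imposes a duty from consent and does not say that only later ADRs count. A reader might also infer that waiver patients contribute no ADRs, but their window is undefined rather than empty.

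The defence does not remove the conflict. Section 11.2 names the eCRF and gives a start date. Expedited reporting has its own sentence, so the eCRF sentence is not merely a pharmacovigilance rule. Nothing in Section 11.2 limits it to the timing of data entry. Source verification cannot settle the question, since monitors hold the same two rules. The eCRF completion guidance, which might settle it, is not among the documents.

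**Conclusion.** The point holds as an internal contradiction on the collection of a primary outcome. Section 11.2, if followed as written, gives the wrong dataset for a retrospective study, and nothing subordinates it to Section 9.3.

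The size is conditional. For a site that applies Section 11.2 literally, most of the ADR window is lost: about 83% to 91% of on-treatment person-time in the base calculation and 70% to 94% under wider assumptions. If ADRs start early, the loss of onsets is nearly complete. These figures rest on assumed start dates, exponential durations and PFS as a stand-in for time on treatment. They count onsets, so an ADR still present at consent might be captured.

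A reader might conclude that the study will miss almost all its ADRs. The documents do not support that as a prediction. Sites following Section 9.3 would record the early events, and the split between sites is unknown. Near-total loss also needs the front-loaded onset assumption.

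**What to change.** 1. In Section 11.2, start the eCRF window for ADRs and fatal adverse events at first dose, whatever the consent date or waiver status, and align it with Section 9.3 by cross-reference.
2. Keep the consent anchor for NIS AE form reporting only, and state the start point that applies to waiver patients.
3. In the SAP rule for completely missing AE onset dates, replace the informed-consent date with the date of first dose. Such ADRs that ended on or after first dose, or have no end date, would then be imputed to first dose and so to the pre-modification period. The report should give their number.

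The cost is a wording change in the protocol, matching eCRF completion instructions and one line of the SAP. The charts are being abstracted anyway, so no new data source is needed.

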9.7 DATA ANALYSIS

9.7.1 Main analysis

All collected data will be analysed separately for patients starting with 40mg and \leq 30mg. Although due to anticipated low sample size in patients starting with \leq 30mg, it will be mainly for exploratory purpose. Baseline demographics will be analysed with descriptive statistics (N, median, mean, 25%, 75% percentile, SD) and compared descriptively between patients who have dose modifications within the first 6 months of Gi(l)otrif[®] treatment and those who do not. All the demographics, safety and efficacy data from this study in real-world setting will be compared with data from LUX-Lung 3 trial in descriptive manner.

Analysis of Safety:

[figure not shown]
Safety analysis will include all patients treated with Gi(l)otrif[®] and be descriptive in nature. Incidence and severity of ADRs according to Common Terminology Criteria for Adverse Events (CTCAE) criteria (version 4.0) ([R15-5988](#)) when available will be summarized and displayed in number/percentage. For patients who had Gi(l)otrif[®] dose modifications within the first 6 months of Gi(l)otrif[®] treatment, frequency and severity of the common ADRs pre- and post-dose modification will be analysed (\geq 40mg vs $<$ 40mg; and \geq 30mg vs $<$ 30mg). Missing or incomplete ADR dates will be imputed according to BI internal SOPs.

Analysis of Effectiveness:

Effectiveness analysis will include all patients treated with Gi(l)otrif[®]. Time on treatment is from the date of first dose of Gi(l)otrif[®] treatment to the date of last dose of Gi(l)otrif[®] treatment. Time to progression is from the date of first dose of Gi(l)otrif[®] treatment to the earliest date of documented progression (clinical, radiographic or both clinical/radiographic progression) or death. Time on treatment and time to progression will be estimated using Kaplan-Meier method, and the median along with two-sided 95% CI will be displayed (use the Greenwood's formula for estimation of standard errors). Log-rank test will be applied to compare between patients with and without dose modifications. Time on treatment and time to progression will be compared between patients who dose reduced to $<$ 40 mg within the first 6 months of Gi(l)otrif[®] treatment and those who remained on Gi(l)otrif[®] 40 mg once daily. This is in analogy to the analysis made on LUX-Lung 3 where a cut-off of 6 months was used as most dose reductions occur during this time.

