## 1 Methods for calculation of derived variables

Age at registration: Year of registration [patient.birthyear] – Year of birth [registration.registered\_at]

Drug-related AE: All AE with relationship to Gi(I)otrif® [ae.gilotref\_relation\_1='yes']

Time on treatment: Date of last administration [endofobservation.date] - Date of first administration of Gi(I)otrif® [baseline.date]. For patients still on treatment, time on treatment will be censored at the date of data collection.

Time to progression (TTP): First date of progression [min(endofobservation.radio\_date, endofobservation.clinic\_date)] - Date of first administration of Gi(I)otrif® [baseline.date]. Patients not known to have a progression will be censored with the date of last contact. For patients still on treatment and without progression, time to progression will be censored at the date of data collection. For patients who stopped treatment and without progression or progression date missing, time to progression will be censored on the last contact date.

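### Section 11.2 lets an event's response to a dose change help decide whether it is recorded as an ADR, so the pre/post ADR comparison can be partly conditioned on the response it measures

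*Protocol*

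**What the plan says.** Protocol 11.2 requires the eCRF to hold all ADRs, all fatal AEs and, in Japan, AEs that may lead to disability. The variable list in 9.3 names ADRs and has no general AE item. On attribution, 11.2 says "The investigator carefully assesses whether an AE constitutes an ADR using the information below". The factors that follow include "pattern of reaction, temporal relationship, de-challenge or re-challenge". The listed arguments for a causal link include "An indication of dose-response (i.e. greater effect size if the dose is increased, smaller effect size if dose is diminished", and those against include "Disappearance of the event even though the study drug treatment continues or remains unchanged". All of them are left to judgment: "Medical judgment should be used to determine the relationship, considering all relevant factors".

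The percentage of subjects with ADRs by severity is a primary outcome (9.3.2.1). For patients whose dose was modified in the first 6 months, 9.7.1 says that "frequency and severity of the common ADRs pre- and post-dose modification will be analysed". The abstract describes this same summary as one of AEs, not ADRs. Section 1 of the SAP derives one related variable, "Drug-related AE: All AE with relationship to" the study drug, by selecting a relationship field equal to yes. Neither 9.9 nor 9.12 mentions that attribution may depend on the response to the dose. The ENCePP checklist (item 6.2) answers No on whether the validity of endpoint measurement is discussed.

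**The concern.** The primary objective asks what dose modification does to the frequency and severity of ADRs. If easing after a reduction helps an event qualify as an ADR, part of the outcome is selected on the effect under study. A prospective study could fix attribution before the response is seen. Here the investigator works from existing records and can see both the reduction and what followed.

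The causality list is reasonable for pharmacovigilance. The difficulty is that the same list also decides which ordinary non-fatal events reach the analysis data. An event that is never entered cannot be recovered later, so no analysis of the planned data could show whether the filter mattered.

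**Working it through.** The plan gives no figure for this point and the safety analysis is descriptive, so there is nothing to reproduce. Three checks follow.

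**1. Direction of each possible error.** Let *pre* and *post* be the recorded percentages of modified patients with the event before and after the dose change.

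- A persisting event is not called an ADR. It is missing from both *pre* and *post*. The difference *pre* − *post* is unchanged, but the ratio *post*/*pre* is too low, so the relative fall is inflated.
- An unrelated event is called an ADR because it eased. It is added to *pre* only, so the absolute and the relative fall are both inflated. The documents give no figure to size this.
- An event is discounted because it faded on an unchanged dose. If it faded before the reduction, *pre* loses it and the fall shrinks. If it arose and faded on the stable lower dose, *post* loses it and the fall grows. The direction is mixed.

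**2. Bound on the first error.** The inputs are the all-grade drug-related percentages in patients who reduced their dose in LUX-Lung 3 (Protocol section 7), taken as assumed values for what this study would record. If *h* is the percentage of patients hidden, then *h* ≤ 100 − *pre*, and the true ratio is (*post* + *h*)/(*pre* + *h*). This is largest at *h* = 100 − *pre*, where it equals (*post* + 100 − *pre*)/100.

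| Event | pre | post | Absolute fall | Recorded ratio | Max. hidden | Largest true ratio |
|---|---|---|---|---|---|---|
| Diarrhoea | 99.2 | 46.7 | 52.5 | 0.47 | 0.8 | 47.5/100 = 0.475 |
| Rash/acne | 88.5 | 38.5 | 50.0 | 0.44 | 11.5 | 50.0/100 = 0.50 |
| Stomatitis | 77.0 | 27.9 | 49.1 | 0.36 | 23.0 | 50.9/100 = 0.51 |
| Nail effects | 44.3 | 36.9 | 7.4 | 0.83 | 55.7 | 92.6/100 = 0.93 |

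These are ceilings, not estimates. They cover all-grade incidence only, and only patients missing from both counts.

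**3. Illustration with assumed labelling.** Suppose every modified patient has the event beforehand, a share *r* still has it afterwards, eased events are always called ADRs, and persisting events are called ADRs with probability *c*. The recorded ratio is *rc*/(*rc* + 1 − *r*).

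- *r* = 0.5: *c* = 0.9 gives 0.45/0.95 = 0.47; *c* = 0.8 gives 0.40/0.90 = 0.44; *c* = 0.7 gives 0.35/0.85 = 0.41. The true ratio is 0.50.
- *r* = 0.6: *c* = 0.9, 0.8 and 0.7 give 0.54/0.94 = 0.57, 0.48/0.88 = 0.55 and 0.42/0.82 = 0.51. The true ratio is 0.60.

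In the most extreme case with *r* = 0.5, the recorded relative fall is 1 − 0.41 = 0.59. Labelling contributes 0.09 of it, and the other 0.50 is assumed resolution. If eased and persisting events are labelled alike (*c* = 1 here), there is no bias. The values of *c* are assumptions.

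**The case against.** The strongest reply is that the list need not work this way. Its items are optional, and the test is only a reasonable possibility of a causal link. Other items suffice without any dose response, for example "The event is known to be caused by or attributed to the drug class", known pharmacology or a plausible time to onset. For diarrhoea, rash and stomatitis these would often settle attribution. The reason for each dose modification is also collected, so an event that prompted a reduction was plausibly attributed to the drug before its response was known. Using ADRs also matches the LUX-Lung 3 figures, which are for drug-related AEs. All of this stands. It limits the likely size and argues for keeping ADRs as the main analysis. It does not remove the dependence, and it is weaker for less typical events.

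A reader might infer several stronger things that the documents do not support:

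- *That persistence after a reduction counts against causality.* Section 11.2 names continuation after withdrawal, with a caveat for prolonged events. A persisting event loses one supporting argument and is not expressly excluded.
- *That only ADRs are collected.* Fatal AEs and the Japanese disability events are also collected, though they hardly touch the pre/post comparison.
- *That the SAP analyses related events only.* The available text defines one derived variable and does not show the planned tables.
- *That losing transient events in unreduced patients biases this comparison.* The 9.7.1 pre/post analysis is confined to patients with dose modifications.

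**Conclusion.** The point holds in limited form. Under 11.2 the response to a dose change may support ADR status, ordinary non-fatal events judged unrelated need not be entered, and 9.7.1 then measures that response in ADRs. The comparison can therefore be partly conditioned on its own result, and the plan does not say so.

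The size is unknown. If this study resembles LUX-Lung 3, omission of persisting events is negligible for diarrhoea and could matter more for rash/acne, stomatitis and nail effects, up to the ceilings in the table. It would distort relative falls and leave absolute falls alone. Mislabelling of unrelated events that eased would inflate both and cannot be sized from the documents. The net effect of the unchanged-dose item has no clear sign.

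It would be too strong to say that the outcome is defined by its answer, or that the expected fall is an artefact. For diarrhoea, stomatitis and rash/acne, hidden persisting events cannot account for most of a fall of the LUX-Lung 3 size. This is a cheap improvement, best made before data entry, and not a defect that invalidates the analysis.

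**What to change.** - **9.7.1:** keep the ADR pre/post analysis as the main one, matched to the drug-related LUX-Lung 3 figures. Add a sensitivity table that repeats it for diarrhoea, rash/acne, stomatitis/mucositis and nail effects regardless of causality. This also reconciles 9.7.1, which refers to ADRs, with the abstract, which refers to AEs.
- **9.3 and 11.2:** ask sites to enter every charted episode of these four event types between first and last dose, with the relationship field completed. The SAP's AE dataset already has that field, and 11.2 already expects sites to keep records of all AEs in the patient files.
- **9.9 and 9.12:** state that ADR attribution may depend on the response to the dose change. State also that this remains for less typical events and for the overall ADR percentage, which the sensitivity table does not cover.

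The cost is a few more chart entries per patient, one extra table, and some unrelated background events in the all-cause version. Safety reporting under 11.2 is unchanged.
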